16.8. Protocol Modifications

Changes in the protocol may be made only by written amendment agreed upon by the sponsor, the regulatory agency, and if pertinent, the EC. As appropriate, the

CONFIDENTIAL AND PROPRIETARY DATA: This document and the information contained herein may not be reproduced, used, or disclosed without written permission from Edwards Lifesciences SA

Investigation Sponsor will submit changes in the protocol to the pertinent regulatory agencies and investigators to obtain approval from the EC.

16.9. Registry completion, termination and close-out

The registry and site Principal Investigators will be notified in writing upon termination or conclusion of the registry. The Investigation Sponsor retains the right to suspend or terminate this registry at any time. The reason for termination will be communicated to sites and authorities as applicable.

The Sponsor shall;

- a) Ensure all registry close-out activities are properly conducted**
- b) Provide a statistical analysis of the data**
- c) Produce a registry report and submit it for review**
- d) Ensure that the registry report, whether for a completed or prematurely terminated registry, is provided to the EC, participating Investigators and regulatory authorities, as required by national regulations**

16.10. Sponsor records

Edwards Lifesciences will maintain accurate, complete, and current records relating to this registry. Records include CRFs, signed and dated Clinical Investigator Agreement, financial disclosure, protocols and protocol amendments, EC approval letters, EC submissions, correspondence, including required reports, and other documents. Edwards will maintain documentation during and after the registry as required by the applicable regulatory requirement(s) but for a minimum of two years after the registry is terminated or completed. Storage of the records may be designated to a third party.

16.11. Audits and inspections

In the event that audits are initiated by the Sponsor or national/international regulatory authorities, the investigator shall allow access to the original medical records and provide all requested information.

16.12. Sponsor reports

Edwards Lifesciences will prepare and submit the following accurate and complete reports to the Investigators, EC and the pertinent regulatory agencies in a timely manner;

- Withdrawal of EC approval will be reported to all EC and the pertinent regulatory agencies as applicable**
- Withdrawal of the pertinent regulatory agencies approval will be reported to investigational centers and EC as applicable**
- A current Investigator list will be submitted to the pertinent regulatory agencies at as applicable**

- Progress reports to the Investigator for the EC and to the pertinent regulatory agencies as required
- A final written report is to be completed and submitted to the EC and the pertinent regulatory agencies after completion or termination of the investigation as applicable
- Use of the devices without informed consent will be reported to relevant authorities as applicable
- Upon request by a reviewing EC or the pertinent regulatory agencies, Edwards will provide current information about any aspect of the investigation

18.1. APPENDIX A: Table of procedures and flowchart

Time Periods and Assessments	Preoperative	Operative	Discharge	30 Days (Phone)	6 Months (180 days)
Informed Consent	X				
Medical History Aortic Valve Etiology and diagnosis	X				
Inclusion Criteria / General Exclusion Criteria	X				
Medical Examination	X		X		X
Height	X				
Weight	X		X		X
Heart rate and Blood Pressure	X		X		X
NYHA	X		X	X	X
Demographics (DOB& gender)	X				
LVEF	X				
Logistic Euroscore I and II	X				
Pregnancy test (If applicable) ¹	X				
Health care utilization (Length of stay ICU and war0064)			X		

Time Periods and Assessments	Preoperative	Operative	Discharge	30 Days (Phone)	6 Months (180 days)
Implant Procedural Data and timing		X			
Intra-operative Exclusion criteria evaluation		X			
12 Lead Electrocardiogram (EKG)²	X		X		X
Transthoracic Echocardiography and Doppler	X ³		X ⁴		X ⁴
Current Anticoagulation Therapy	X		X		X
Coagulation profile: INR and PT⁵	X		X		X
Blood Studies RBC, WBC, HGB, HCT, Reticulocytes, Platelet counts, Serum Creatinine	X		X		X
Fitness for hospital discharge			X		
Quality of Life (QoL): EQ-5D SF-36	X				X
Adverse Events		X	X	X	X

1 - Pregnancy test is required for female subjects who are not post-menopausal or surgically sterile (urine)

2 - For EKG machine generated reports the Investigator must verify that the cardiac rhythm is correct and sign and date the final EKG report

3 - If available Pre-op echocardiography within 3 months of planned implant date and including echocardiographic data in the format required per the echocardiography guidelines

4 - If available echocardiography data will be collected

5 - Required only if patient is being treated with a coumadin derivation medication

18.2. APPENDIX B: registry abbreviations

Abbreviations of Terms			
ACC	American College of Cardiology	GCP	Good Clinical Practice
ADE	Adverse Device Effect	ICE	Intra Cardiac Echocardiography
AE	Adverse Event	IFU	Instructions for Use
AHA	American Heart Association		
AI	Aortic Insufficiency	LV	Left Ventricle
AS	Aortic Stenosis	LVEF	Left Ventricle Ejection Fraction
AVR	Aortic Valve Replacement	LVOT	Left Ventricular Outflow Tract
BMI	Body Mass Index	LVMI	Left Ventricular Mass Index
BSA	Body Surface Area	NSVD	Nonstructural Valve Dysfunction
		NYHA	New York Heart Association
		POD	Post Operative Days
CEC	Clinical Events Committee		
CHF	Congestive Heart Failure	PPM	Patient Prosthesis Mismatch
CI	Cardiac Index	PTFE	Polytetrafluoroethylene
CO	Cardiac Output	PVL	Perivalvular Leak
CPBT	Cardiopulmonary Bypass Time	SAE	Serious Adverse Event
eCRF	Electronic Case Report Form	SADE	Serious Adverse Device Effect
XCT	Cross Clamp Time	SF-36	Short Form-36 Health Survey
		SLDH	Serum Lactate dehydrogenase
EC	Ethics Committee	STS	Society of Thoracic Surgeons
ECG/EKG	Electrocardiogram	SVD	Structural Valve Deterioration
EOA	Effective Orifice Area	TEE	Transesophageal echocardiogram
EOAI	Effective Orifice Area Index	TTE	Transthoracic echocardiogram
EQ-5D	EU Quality of Life-5 Dimensions	USADE	Unanticipated Serious Adverse Device Effect
FMEA	Failure Modes and Effects Analysis		

18.3. APPENDIX C: Registry Definitions

Device Explant - Explant is defined as a re-intervention resulting in removal of the implanted valve after the patient left the operating room with an implanted valve, after the index procedure

Device Deficiency - Inadequacy of a medical device with respect to its identity, quality, durability, reliability, safety or performance. **NOTE:** Device deficiencies include malfunctions, use errors, and inadequate labeling.

Device Removal - The excision of the investigation bioprosthesis before the EDWARDS INTUITY Elite Valve System procedure was completed. The heart *was not* restarted with the bioprosthesis implanted. Patient still IN the operating room.

EDWARDS INTUITY Elite Valve Device Technical Success - The successful delivery and deployment of a registry valve and delivery system and subject leaving the operating room with valve in place.

EDWARDS INTUITY Elite Valve Procedural Success - is defined as device technical success followed by the absence of adverse events requiring device reoperation, requiring implantation of permanent pacemaker (with baseline sinus rhythm and no other conduction issues), or subject death, within discharge or 10 days post index procedure whichever comes first.

Enrollment cohort:

A subject will be considered enrolled into the registry when he/she has signed the informed consent, met all the registry eligibility criteria.

Implant failure - is defined as a re-intervention resulting in removal of the implanted valve with the patient still in OR, after the index procedure

Index Procedure - Surgical replacement of the aortic valve.

New York Heart Association Classification

- Class I: Patients with cardiac disease but without resulting limitations of physical activity.
- Class II: Patients with cardiac disease resulting in slight limitation of physical activity. Patients are comfortable at rest. Ordinary physical activity results in fatigue, palpitation, dyspnea, or angina pain.
- Class III: Patients with cardiac disease resulting in marked limitation of physical activity. They are comfortable at rest. Less than ordinary physical activity causes fatigue, palpitation dyspnea, or angina pain.

Class IV: Patients with cardiac disease resulting in inability to carry on any physical activity without discomfort. Symptoms of cardiac insufficiency or of the angina syndrome may be present even at rest. If any physical activity is undertaken, discomfort is increased.

Protocol deviations - The protocol deviations are defined as deviations in the informed consent improperly obtained (not signed & dated, not consented); inclusion/exclusion criteria (eligibility and/or intra-operative criteria); safety as UADE / USADE not reported within 24 hours of the investigator first learning of the event without documentation.

Pre-operative Screen Failure - A patient with an ID number assigned, and who has signed his/her informed consent and does not meet all eligibility inclusion criteria or who meets at least one of the eligibility exclusion criteria.

Intra operative Screen Failure - A patient with an ID number assigned and who meets at least one of the intra-operative exclusion criteria.

Subject - A patient that signs an informed consent to participate in a clinical investigation.

Subject Withdrawal - A subject that decides not to participate in the investigation after signing an informed consent form.

Per protocol cohort: A subject will be considered enrolled into the registry when he/she has signed the informed consent, met all the registry eligibility criteria, and no intra-operative exclusion criteria; and leaves the operating room with the registry valve in place and had an AVR MIS surgery procedure.

Withdrawal by Investigator - A subject who consents to participate in the investigation but is withdrawn by the Investigator before or after enrollment in the investigation.

Withdrawal - Subjects may discontinue participation at any time by withdrawing informed consent.

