7. REGISTRY ENDPOINTS

7.1. Primary endpoint:

- Cross clamp time (cumulative XCT during the SAME operation should be recorded)

7.2. Secondary endpoints:

- Cardiopulmonary bypass time
- Device technical success rate (defined as the successful delivery and deployment of the valve and delivery system and subject leaving the operating room with valve in place)
- First attempt success rate
- ICU and Hospital Length of Stay
- Hemodynamic performance (mean gradient, peak gradient, effective orifice area [EOA], EOA index, performance index, cardiac output [CO], cardiac index [CI], valvular regurgitation [including paravalvular leak] confirmed by and Core lab evaluation) at Discharge and 6 months (if available)

7.3. Patient related endpoints:

- NYHA functional class compared to baseline
- Change in Quality of Life questionnaire SF-36 and EQ-5D from Baseline to 6 months, if applicable
- Fitness for hospital discharge.
 - The criteria for Fitness for hospital discharge ¹⁹ are:
 - Hemodynamic stability
 - Independent ambulation
 - No fever or obvious infections and wound clean
 - Independent feeding
 - Normal voiding
 - Pain control on oral medications
 - Meeting one criteria will provide one point to the score. The maximum is 6 points. According to this scoring system, the patient will be considered fit for discharge when the score is the maximum (i.e. 6). The post-operative day on which the patient meets the maximum score (i.e. 6) will be considered as the day at which the patient was fit for hospital discharge and will be recorded.
 - The composite score will be assessed on the day of discharge based on chart data.

7.4. Safety endpoints:

The safety endpoints consist of:

- All cause mortality
 - Study valve-related mortality
- Thromboembolism:
 - Stroke
 - TIA
 - Non cerebral embolism
- Valve Thrombosis
- Major Bleeding event
- Endocarditis (study valve)
- Structural valve deterioration
- Non Structural valve deterioration
 - Paravalvular Leak minor
 - Paravalvular Leak major
 - Other non SVD
- Hemolysis
- Reoperation
 - Trial valve reoperation
- Study valve explants

- **Implant-related new or worsened cardiac conduction disturbance requiring permanent pacemaker implant**
- **Renal Failure**
- **Respiratory Failure**
- **Deep Sternal Wound infection**

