9.6. Operative Procedures

In the operating room, the intra-operative and eligibility exclusion criteria will be assessed by careful examination of the valve anatomy, valve condition and associated structures.

All data collected on the operative procedure will be documented into the eCRF. Subjects will be prepped for a minimally invasive surgical approach used for isolated aortic valve replacement. Minimal invasive surgery (MIS) is defined as a non-full sternotomy approach such as partial hemi-sternotomy and right anterior thoracotomy.

A detailed description of device preparation and use is provided in the Instructions for Use (See Appendix I for both the EDWARDS INTUITY Elite Valve, Model 8300AB and EDWARDS INTUITY Elite Delivery System, Model 8300DB. Investigators will be advised of the EDWARDS INTUITY Elite Valve System device preparation and use techniques per the Instructions for Use (IFU) during the mandatory training program.

The procedure will be considered a technical success if the subject leaves the Operating Room with the EDWARDS INTUITY Elite valve in place.

The procedure will be considered a procedural success in case of technical success followed by the absence of adverse events requiring device reoperation, requiring implantation of permanent pacemaker (with baseline sinus rhythm and no other conduction issues), or subject death, within discharge or 10 days post index procedure whichever comes first.

The number of attempts (maximum 2) and final outcome of each EDWARDS INTUITY Elite Valve placement attempt shall be documented on the Device Performance form in CRF.

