9.11.2. EDWARDS INTUITY ELITE VALVE EARLY POST-OPERATIVE EXPLANT

Explant of EDWARDS INTUITY Elite Valve is the removal of the registry valve after the index EDWARDS INTUITY Elite Valve System procedure is completed and the patient is physically transported from the operating room with an implanted valve in place. The valve is explanted by accessing the aortic valve site and exposing the valve. Once exposure has been achieved, the surgeon should use a scalpel to cut the three sutures in the inter-commissural region on the sewing cuff of the valve. Once the three sutures have been removed, the surgeon should perform a circumferential blunt dissection around the registry valve. Once a blunt dissection is complete, use forceps to grasp the valve at the commissure and lift the study valve upward from the annulus.

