12.1.2. PER PROTOCOL COHORT

The per protocol cohort will consist of all enrolled patients that leave the operating room with the registry valve in place and had an AVR MIS surgery procedure. All summaries of the safety endpoints and other safety data will be based on the per protocol cohort. The summaries of the primary, secondary and patient related endpoints will also be based on the per protocol cohort.

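### Technical success and per protocol entry do not say how a death in the operating room after valve deployment is classed, and 12.1.2 and 12.3 disagree on the cohort for safety

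*Combined protocol and SAP*

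**What the plan says.** **Technical success.** Appendix C defines it as "The successful delivery and deployment of a registry valve and delivery system and subject leaving the operating room with valve in place". Section 7.2 lists it as a secondary endpoint, "defined as the successful delivery and deployment of the valve and delivery system and subject leaving the operating room with valve in place", and the synopsis matches these in substance. Section 9.6 is shorter: "The procedure will be considered a technical success if the subject leaves the Operating Room with the EDWARDS INTUITY Elite valve in place". None of the four statements mentions survival.

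**Per protocol cohort.** Section 12.1.2 states: "The per protocol cohort will consist of all enrolled patients that leave the operating room with the registry valve in place", with the further condition of a minimally invasive procedure. Appendix C uses the same test: "leaves the operating room with the registry valve in place and had an AVR MIS surgery procedure".

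**Use of that cohort.** Section 12.1.2 continues: "All summaries of the safety endpoints and other safety data will be based on the per protocol cohort". It then adds: "The summaries of the primary, secondary and patient related endpoints will also be based on the per protocol cohort".

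**Text that points elsewhere.**
- 12.2.3 reports technical and procedural success as a percentage of enrolled patients.
- 12.3 divides events within 30 days by the number of enrolled subjects.
- Table 2 defines all-cause mortality over all registry subjects.
- 9.4 collects adverse events from the time the subject is in the operating room.

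**What leaving may mean.** Section 9.11.2 describes a completed index procedure as one after which "the patient is physically transported from the operating room with an implanted valve in place". Section 9.11.1 likewise identifies intra-operative removal by the patient not yet having been transported out.

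**Procedural success.** Section 9.6 and Appendix C make death, by discharge or day 10 (whichever is first), a procedural failure. Section 12.2.3 tabulates this measure, but neither the synopsis nor section 7 lists it as an endpoint.

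**The concern.** One phrase does two jobs: it defines a success endpoint and it admits subjects to an analysis cohort. No passage says how to class a subject who dies in the operating room with the valve deployed. Procedural success names death explicitly and technical success does not, so a reader cannot assume that survival is implied.

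Two analysts could follow the plan faithfully and report the same death differently. One would count it as a device success. The other would place it outside the cohort used for safety. All-cause mortality is the first-listed safety endpoint, and section 4.1 includes frame-related damage to the aortic wall or annulus among the risks that could be unique to this system. Section 2.2 says the results will support publications and marketing information, so the rule should be fixed before any such case arises.

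**Working it through.** The plan gives no operative death rate, 30-day death rate or expected technical success rate, so it has no figure of its own to reproduce on this point. Its one calculated figure, power above 90% in 12.5, is not affected. With 300 against 479 subjects, a 15-minute difference and an SD of 16.0 taken for both groups, the noncentrality is 15 / [16.0 × √(1/479 + 1/300)] = 12.73. Power is then about 100%, which meets the stated bound.

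**Step 1: class one on-table death after deployment under each reading (minimally invasive approach, no conversion, valve still in place).**

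| Item | Leaving = transported out | Leaving = leaving alive |
|---|---|---|
| Device technical success | success | failure |
| Procedural success | failure | failure |
| In per protocol cohort | yes | no |
| 30-day mortality under 12.1.2 | counted | lost |
| 30-day mortality under 12.3 and Table 2 | counted | counted |
| Kaplan-Meier rates | counted | lost if 12.1.2 applies |

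Two cells need comment. Section 12.3 names the denominator for early events but not the cohort that supplies the events. If 12.1.2 governed the numerator, the death would be lost while the denominator stayed at enrolled subjects. For the Kaplan-Meier rates 12.3 names no cohort, so 12.1.2 applies by default.

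**Step 2: the denominator of technical success.** Section 12.1.2 puts secondary endpoints on the per protocol cohort, and 12.2.3 puts technical success on enrolled patients. Under 12.1.2 the rate is close to 100% by construction, because the main condition for success is also the condition for entry.

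**Step 3: size.** Assume 300 subjects, k on-table deaths after deployment, all other implants successful, and 3 further deaths by day 30. Only the 300 comes from the plan.
- Technical success is 300/300 = 100% if the deaths count as success. Otherwise it is (300 − k)/300 = 99.7%, 99.3% or 99.0% for k = 1, 2 or 3.
- Early mortality with the deaths kept is (3 + k)/300 = 1.33%, 1.67% or 2.00%.
- Early mortality with the deaths dropped is 3/(300 − k), that is 3/299 = 1.00%, 3/298 = 1.01% or 3/297 = 1.01%.
- With k = 1 and no other death, the comparison is 1/300 = 0.33% (exact 95% CI 0.01% to 1.84%) against 0/299 = 0% (0% to 1.23%).
- Per death, the shift is 1/300 = 0.33 percentage points.

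**Step 4: how likely a case is.** The chance of at least one in 300 is 1 − (1 − p)^300. For assumed p of 0.1%, 0.25%, 0.5% and 1% this is 26%, 53%, 78% and 95%.

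**The case against.** The strongest reply is that the plan already protects mortality. Section 12.3 uses enrolled subjects, Table 2 counts all deaths of registry subjects, and 9.4 starts event collection in the operating room. The protocol's own usage in 9.11.1 and 9.11.2 is physical transport. On that reading the subject stays in the per protocol cohort and the death is counted everywhere. The death would also fail procedural success, which 12.2.3 reports beside technical success.

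Most of this stands. A reader might infer that the per protocol cohort carries every mortality summary, so that 30-day mortality will be biased low. The documents do not support that. It requires both that leaving means leaving alive and that 12.1.2 prevails over 12.3, and neither is settled.

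A reader might also infer a large relative bias. If 3 of 6 deaths in 300 occurred on the table and were dropped, 3/297 = 1.01% would replace 2.00%, an understatement of 49%. That needs both conditions above, and half of all 30-day deaths in the operating room after deployment. It is an assumed extreme, not an expected bias.

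The reply does not remove the defect. On the transport reading a death is still a success on a listed endpoint, and the measure that would catch it is not listed. On the other reading 12.1.2 and 12.3 contradict each other, and the Kaplan-Meier rates have no stated cohort except through 12.1.2.

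**Conclusion.** The point holds in a limited form. The definitions leave an on-table death after deployment unclassified, and each reading has a cost. Transport makes the death a technical success. Leaving alive puts it outside the cohort that 12.1.2 uses for safety, in conflict with 12.3 and Table 2. The separate contradiction between 12.1.2 and 12.2.3 over the denominator of technical success is certain on the text.

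The size is about 0.33 percentage points per death in 300 subjects, in technical success or in early mortality depending on the reading. It is zero if no such death occurs. These figures rest on assumed counts, because the documents give no rate. Any loss from the 30-day rate is conditional, as set out above. The numerical effect is small, but the outcome is serious and the correction is simple, so it should be made before analysis.

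**What to change.** 1. In the synopsis, 7.2, 9.6 and Appendix C, define technical success as the subject leaving the operating room alive with the registry valve in place.
2. In 12.1.2, base mortality and all other safety summaries on all enrolled subjects in whom the procedure was started. Include deaths on the table and deaths after valve removal or conversion to full sternotomy. Admitting on-table deaths to the per protocol cohort would not be enough, since removal or conversion would still take a subject out of it.
3. In 12.3, name this cohort for both the numerator and the denominator of the early rates, and for the Kaplan-Meier rates, with on-table deaths as events at day 0. List intra-operative deaths separately.
4. Reconcile 12.1.2 with 12.2.3 so that technical success is not computed within a cohort defined by almost the same condition.
5. In 12.1.2 and Appendix C, say how an on-table death is classed for per protocol entry.

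The amendment must also say when the procedure starts. Section 9.6.1 already gives 30-day follow-up to subjects with a failed implant attempt, or with conversion after the valve implant procedure is initiated. Using that initiation as the starting point would need no new data.

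The cost is a few words in each place. Technical success may come out slightly lower and early mortality slightly higher.
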